12.0 AUDIT AND INSPECTION

Study sites and study documentation may be subject to Quality Assurance audit during the course of the study by the sponsor or its nominated representative. In addition, inspections may be conducted by regulatory authorities at their discretion.

13.0 ETHICS, REGULATORY, INFORMED CONSENT AND PATIENT CONFIDENTIALITY

13.1 Independent Ethics Committee or Institutional Review Board

Before initiation of the study at each study center the protocol, the ICF, other written material given to the participants, and any other relevant study documentation will be submitted to the appropriate IEC/IRB. Written approval of the study and all relevant study information must be obtained before the study center can be initiated or the study drug is released to the investigator. Any necessary extensions or renewals of IEC/IRB approval must be obtained for changes to the study such as amendments to the protocol, the ICF or other study documentation. The written approval of the IEC/IRB together with the approved ICF must be filed in the study files.

The investigator will report promptly to the IEC/IRB any new information that may adversely affect the safety of the participants or the conduct of the study. The investigator will submit written summaries of the study status to the IEC/IRB as required. On completion of the study, the IEC/IRB will be notified that the study has ended.

13.2 Regulatory Authorities

Relevant study documentation will be submitted to the regulatory authorities of the participating country, according to local/national requirements, for review and approval before the beginning of the study. On completion of the study, the regulatory authorities will be notified that the study has ended.

13.3 Ethical Conduct of the Study

The investigator(s) and all parties involved in this study should conduct the study in adherence to the ethical principles based on the Declaration of Helsinki, GCP, ICH guidelines, and the applicable national and local laws and regulatory requirements.

13.4 Informed Consent

The process of obtaining informed consent must be in accordance with applicable regulatory requirement(s) and must adhere to GCP.

The investigator is responsible for ensuring that no participant undergoes any study related examination or activity before that subject has given written informed consent to participate in the study.

The investigator or designated personnel will inform the participant of the objectives, methods, anticipated benefits and potential risks and inconveniences of the study. The participant should be given every opportunity to ask for clarification of any points s/he does not understand and, if necessary, ask for more information. At the end of the interview, the participant will be given ample time to consider the study. Participants will be required to sign and date the ICF. After signatures are obtained, the ICF will be kept and archived by the investigator in the investigator's study file. A signed and dated copy of the subject ICF will be provided to the participant or their authorized representative.

It should be emphasized that the participant may refuse to enter the study or to withdraw from the study at any time, without consequences for their further care or penalty or loss of benefits to which the participant is otherwise entitled. Subjects who refuse to give or who withdraw written informed consent should not be included or continue in the study.

If new information becomes available that may be relevant to the participant's willingness to continue participation in the study, a new ICF will be approved by the IEC(s)/IRB(s) (and regulatory authorities, if required). The study participants will be informed about this new information and reconsent will be obtained.

13.5 Subject Confidentiality

Monitors, auditors, and other authorized agents of the sponsor and/or its designee, the IEC(s)/IRB(s) approving this research, and the Australian Therapeutic Goods Administration (TGA), as well as that of any other applicable agency(ies), will be granted direct access to the study participants' original medical records for verification of clinical study procedures and/or data, without violating the confidentiality of the participants to the extent permitted by the law

and regulations. In any presentations of the results of this study or in publications, the participants' identity will remain confidential.

14.0 DATA AND SAFETY MONITORING

The study principal investigator and Research Patient Coordinator will monitor for serious toxicities on an ongoing basis. Once the principal investigator or Research Patient Coordinator becomes aware of an adverse event, the AE will be reported to the Sponsor.

15.0 PHARMACOKINETIC STUDIES

Blood samples will be drawn from participants for pharmacokinetic analysis at 15- and 30-minutes pre-dose and then 0.5, 1, 2, 4, 6, 8, 12 and 24 hours post drug administration on day 1 (SAD and MAD cohort) and day 3 (MAD cohort).

Pharmacokinetic analysis will be performed using validated analytic method.

16.0 STATISTICAL ANALYSIS

Demographics and baseline characteristics will be tabulated and summarized by SAD/MAD dose level. Physical examination and medical/surgical history data will be listed by participant.

All clinical safety and tolerability data will be listed for each participant and summarized by dose. Vital signs and ECG parameters will be tabulated and summarized by SAD/MAD dose level. Laboratory values will be listed, along with comments as to clinical significance for values outside the laboratory's normal ranges.

Treatment-emergent adverse events, following the investigational product dosing, will be listed and summarized by dose level. All adverse events reported in this study will be coded using MedDRA.

Individual plasma concentrations and blood collection times will be listed by participant. Summaries of concentration data will include mean, standard deviation and coefficient of variation by SAD/MAD dose level at each scheduled collection time. Summaries of PK parameters by SAD/MAD dose level will include mean, SD and CV.

17.0 RECORD RETENTION

[figure not shown]
Essential documents are those documents that individually and collectively permit evaluation of the study and quality of the data produced. After completion of the study (end of study defined as the date of the last visit of the last participant), all documents and data relating to the study will be kept in an orderly manner by the investigator in a secure study file. This file will be available for inspection by the sponsor or its representatives. Essential documents should be retained for 2 years after the final marketing approval in an ICH region or for at least 2 years since the discontinuation of clinical development of the investigational product. It is the responsibility of the sponsor to inform the study center when these documents no longer need to be retained. The investigator must contact the sponsor before destroying any study related documentation. In addition, all participant

medical records and other source documentation will be kept for the maximum time permitted by the hospital, institution, or medical practice.

[figure not shown]
The sponsor must review and approve any results of the study or abstracts for professional meetings prepared by the investigator(s). Published data must not compromise the objectives of the study.

18.0 SCHEMA

[figure not shown]
SAD – Low Dose Cohort

SAD

MAD

TEAE	Treatment Emergent Adverse Event
TLF	Tables, Listings and Figures
WHO	World Health Organization

This document is confidential.

2. Purpose

The purpose of this statistical analysis plan (SAP) is to ensure that the data listings, summary tables and figures which will be produced, and the statistical methodologies that will be used, are complete and appropriate to allow valid conclusions regarding the study objectives.

This SAP is based on the following documents:

- Protocol V3, dated 30-Jan-2020.
- Addendum to Clinical Protocol (version 29MAY2019_v2), dated 31-Mar-2020
- Electronic Case Report Form (eCRF) version 4.00, dated 19-Mar-2020.

2.1. Responsibilities

Syneos Health will perform the statistical analyses and are responsible for the production and quality control of all tables, listings, figures (TLFs) and Pharmacokinetic (PK) analysis.

2.2. Timings of Analyses

Interim Analysis:

Interim PK analysis may be performed by the pharmacokineticist after the completion of individual cohorts.

Final Analysis:

The primary analysis of safety and PK is planned after all subjects complete the final study visit or terminate early from the study.

This document is confidential.

3. Study Objectives

3.1. Primary Objective

The primary objective of this study is:

- To determine the safety and tolerability of 4 single and multiple ascending doses of LSALT peptide in healthy participants.

3.2. Secondary Objective

The secondary objective of this study is:

- To evaluate the pharmacokinetics and pharmacodynamics of LSALT peptide in healthy participants.

3.3. Brief Description

This is a double-blind, placebo-controlled, randomized, adaptive design single and multiple ascending dose study to evaluate the safety and pharmacokinetics of LSALT peptide in healthy participants.

To establish a safe starting dose of LSALT peptide, unblinded low dose escalation will first be performed in a small cohort of participants. 0.01 mg of LSALT peptide will be administered intravenously (IV) once. If no adverse effects are observed following 72 hours, subsequent single (n=1) participants will be administered escalating doses of 0.1 mg, 0.3 mg and 0.5 mg every 72 hours. If no adverse effects are observed at the 0.5 mg dose, then the study will proceed to the first cohort of 8 participants (6 active treatment, 2 placebo per dose level) who will receive 1.0 mg of LSALT peptide in a double-blinded fashion. Safety, tolerability, PK and PD will be assessed before escalating to the next cohort. Dosing will be completed in two sequential cohorts of 8 participants using doses of 2.5 mg and 5.0 mg. The first 2 participants in each blinded cohort will act as sentinels (1 treatment, 1 placebo) who must show no adverse effects before continuing the study under the current design.

Once safety, PK and PD data are completed in the single ascending dose (SAD) cohort, and the LSALT peptide is determined to be safe and well-tolerated by the Safety Review Committee (SRC), the multiple ascending dose arm of the study will proceed. The multiple ascending dose arm will consist of 3 cohorts of 8 participants receiving 3 independent doses of the LSALT peptide or placebo once or twice daily for 3 consecutive days. The doses for this arm of the study will consist of the 3 highest doses determined by the SRC to be safe in the SAD cohort. The first cohort will receive drug in a double-blinded fashion. Safety, tolerability, PK, and PD will be assessed before escalating to the next cohort. Each cohort will consist of 6 active treatment, 2 placebo per dose level. The first 2 participants in each cohort will act as sentinels (1 treatment, 1 placebo) who must show no adverse effects before continuing the study under the current design.

3.4. Subject Selection

Approximately 52 healthy male and female subjects, aged 18-55 years, are planned to be enrolled into the study.

3.5. Determination of Sample Size

No prospective calculations of statistical power have been made. The sample sizes of 4 subjects (low dose cohort), 24 subjects for the SAD portion and 24 subjects for the MAD portion of this study have been selected to provide information on safety, tolerability, PK and PD following single and multiple doses of LSALT peptide.

This document is confidential.

3.6. Treatment Assignment

All subjects enrolled in this study will receive either LSALT peptide or placebo. The planned dose levels are as follows.

Low Dose (unblinded):

Cohort	Dose	Number of Subjects Receiving LSALT	Number of Subjects Receiving Placebo
Low Dose	0.01 mg	1	0
Low Dose	0.1 mg	1	0
Low Dose	0.3 mg	1	0
Low Dose	0.5 mg	1	0

SAD (blinded):

Cohort Number	Dose	Number of Subjects Receiving LSALT	Number of Subjects Receiving Placebo
1 (sentinel group)	1.0 mg	1	1
1	1.0 mg	5	1
2 (sentinel group)	2.5 mg	1	1
2	2.5 mg	5	1
3 (sentinel group)	5.0 mg	1	1
3	5.0 mg	5	1

MAD (blinded):

Cohort Number	Dose	Number of Subjects Receiving LSALT	Number of Subjects Receiving Placebo
4 (sentinel group)	1.0 mg	1	1
4	1.0 mg	5	1
5 (sentinel group)	2.5 mg	1	1
5	2.5 mg	5	1
6 (sentinel group)	5.0 mg	1	1
6	5.0 mg	5	1

TBD = to be determined.

3.7. Randomization and Blinding

Randomization:

Computer generated randomization schedules will be prepared prior to the start of the study. The schedules will be generated through the statistical analysis system (SAS) software, version 9.4. Block randomization will be used.

This document is confidential.

Low Dose Subjects will receive only LSALT peptide. SAD and MAD subjects will be randomly assigned to receive either LSALT peptide or matching placebo in a ratio of 3:1 (active: placebo). A Randomization Plan will be created (which includes provisions for replacement subjects), and the randomization of eligible study participants will be managed as per the plan.

In the event of participant drop-out, participants from the reserve pool will be enrolled in the study and randomized. For subjects who are replaced the replacements should take the same treatment assignment as the original subject to ensure that the planned treatment allocation ratio is retained.

Blinding:

Participants and the study investigators/personnel will be blinded except for initial low doses of LSALT in single subjects which will be open-label. This is a third-party blinded study whereupon the pharmacist (or designate) preparing the LSALT peptide or placebo for infusion will be unblinded.

This document is confidential.

4. Endpoints

4.1. Safety Endpoints (Primary)

The primary safety endpoints are:

- Incidence of AEs.
- Clinical laboratory test results (hematology, chemistry, coagulation and urinalysis).
- Vital sign measurements
- 12 lead electrocardiogram (ECG) readings

4.2. Pharmacokinetic Endpoints (Secondary)

The secondary PK endpoints are:

- Plasma LSALT concentrations.
- Plasma LSALT PK parameters.

This document is confidential.

5. Analysis Populations

All subjects' inclusion status into each analysis population will be determined after database lock and prior to unblinding for the final analysis.

5.1. Intent-to-Treat Population

The Intent-to-Treat (ITT) Population will comprise all randomized subjects and will be based on the randomized treatment, regardless of which treatment the subject actually received. The ITT Population will be used for all summaries of baseline and demographic data. In addition, all listings will be produced for the ITT Population.

5.2. Safety Population

The Safety Population will comprise all randomized subjects who receive any amount of study drug and will be based on the actual treatment received, if this differs from that to which the subject was randomized. The Safety Population will be used for the summaries of all safety and tolerability.

5.3. Pharmacokinetic Concentration Population

The PK Concentration Population will comprise all subjects who receive any amount of LSALT, who have at least one quantifiable PK concentration and will be based on the actual treatment received, if this differs from that to which the subject was randomized. Subjects who receive only placebo will be excluded from the PK Concentration Population. The PK Concentration Population will be used for the summaries of all PK concentration data.

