3.5 Drug Metabolism and Pharmacokinetics

Plasma levels of LSALT peptide were measured post-intravenous dosing of 100, 250 and 450 mg/kg in rats. Terminal elimination half-lives of 0.66 – 1.17 hr and MRT_{obs} values of 0.58 – 0.85 hr were observed for LSALT peptide. The AUC_{0- ∞} was linear and close to proportional with dose.

LSALT peptide is stable in human plasma for up to 90 minutes with no detectable metabolic/proteolytic fragments as measured by mass spectrometry. LSALT peptide is undetectable in whole blood in the absence of phosphoric acid due to red or white blood cell binding. In human whole blood, 90% or more of the LSALT peptide is contained within the cellular compartment. LSALT peptide however is compatible with blood and does not induce red blood cell hemolysis. Work is ongoing to identify LSALT peptide volume of distribution, tissue biodistribution, and excretion.

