8.3. Summary of PK Variables

Concentration:

Plasma concentrations will be listed and summarized, by nominal sampling time, and cohort/actual treatment. Concentrations below the quantification limit (BLQ) will be set to zero in summary tables. BLQ will be displayed in listings.

Individual subject and mean \pm SD profiles of the plasma concentration-time data will be plotted by dose level/cohort using actual and nominal times, respectively. These profiles will be presented on both linear-linear and log-linear scales.

This document is confidential.

For individual plots the BLQ values that occur in a profile before the first measurable concentration will be set to zero, and the BLQ values that occur after first measurable concentration will be set to missing. For mean plots, BLQ will be set to zero.

Parameters:

Plasma PK parameters will be listed and summarized descriptively by dose level/cohort.

For derivation of plasma pharmacokinetic parameters, the BLQ values that occur in a profile before the first measurable concentration will be set to zero. The BLQ values that occur after first measurable concentration will be set to missing.

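### The PK Concentration Population drops LSALT recipients whose samples are all below quantification, so descriptive mean concentrations can only be raised or left unchanged

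*SAP*

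**What the plan says.** SAP 5.3 builds the PK Concentration Population from subjects who receive any LSALT and "who have at least one quantifiable PK concentration". It then states: "The PK Concentration Population will be used for the summaries of all PK concentration data".

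SAP 8.3 gives the handling of BLQ values: "Concentrations below the quantification limit (BLQ) will be set to zero in summary tables". For the figures it adds: "For mean plots, BLQ will be set to zero".

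The group size comes from SAP 3.3. The SAD part starts with a "first cohort of 8 participants (6 active treatment, 2 placebo per dose level) who will receive 1.0 mg of LSALT peptide", and for the MAD part: "Each cohort will consist of 6 active treatment, 2 placebo per dose level". SAP 6.1 lists the low-dose subjects (0.01 to 0.5 mg) without summarising them, so 1.0 mg is the lowest dose with a mean. SAP 6.1 and the shells for the concentration tables also require a geometric mean and geometric CV.

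The formal dose comparison, the power model in SAP 8.4, works on PK parameters. These belong to the separate PK Parameters Population of SAP 5.4.

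**The concern.** The two SAP rules treat the same kind of result in opposite ways. A recipient with one quantifiable sample stays in and contributes zeros at every other BLQ time point. A recipient with no quantifiable sample contributes nothing. Entry thus depends on the outcome being summarised, and the profiles removed are those with the lowest measured values. The SAP gives no reason for this and plans no summary that puts these recipients back. Protocol 16.0 plans concentration summaries by dose level without any condition on quantifiability.

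The documents make the case plausible without showing that it will occur. Protocol 3.5 says: "In human whole blood, 90% or more of the LSALT peptide is contained within the cellular compartment". The assay is of plasma. In SAP 8.1 every post-dose sample on a dosing day is timed from the end of the infusion, and the rat half-lives in Protocol 3.5 are 0.66 to 1.17 hours.

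At stake is the reading of the concentration tables and mean plots. A mean over a selected subset would stand under the dose-group label, with a smaller n and possibly a smaller SD.

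**Working it through.** **Inputs.** Eight participants per cohort at 3:1 (SAP 3.3 and 3.7); BLQ = 0 in tables and mean plots (SAP 8.3); entry rule from SAP 5.3. The documents state no lower limit of quantification, BLQ rate or expected concentration.

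**The plan's own figure.** 8 × 3/4 = 6 LSALT recipients per dose level, as stated. The total 4 + 24 + 24 = 52 also agrees.

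**Effect on the arithmetic mean.** Let S be the sum of concentrations at one time point, with BLQ = 0 and no missing samples, and let k be the number of recipients who are BLQ throughout. These k recipients add zero to S.

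- Mean over all recipients: S/6.
- Mean over the SAP 5.3 population: S/(6 − k).
- Ratio of the second to the first, wherever S > 0: 6/(6 − k).

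The last column shows what a reader would see by eye if the true ratio of the 5 mg mean to the 1 mg mean were 5 (an illustration) and the exclusions fell only at 1 mg.

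| k | 6/(6 − k) | Rise in mean | Apparent 5 mg : 1 mg ratio |
|---|---|---|---|
| 0 | 1.00 | 0% | 5.00 |
| 1 | 6/5 = 1.20 | 20% | 5/1.20 = 4.17 |
| 2 | 6/4 = 1.50 | 50% | 5/1.50 = 3.33 |
| 3 | 6/3 = 2.00 | 100% | 5/2.00 = 2.50 |

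The ratio is never below 1, so the direction does not depend on k. If all six were BLQ, the dose level would have no subjects and no mean.

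**Effect on spread, by example.** Five recipients at 10 and one all-BLQ give a mean of 50/6 = 8.33 and an SD of 4.08 over all six. Under SAP 5.3 the same data give a mean of 10 and an SD of 0.

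**How often the rule would act.** Let q be the probability that a recipient is all-BLQ (an assumption, since the documents give none). The chance that at least one of six is dropped is 1 − (1 − q)^6: 0.114 for q = 2%, 0.265 for 5%, 0.469 for 10% and 0.738 for 20%.

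**The case against.** **The size is hypothetical.** This stands. The percentages follow from assumed values of k, and one quantifiable sample is enough to keep a subject in. The first post-dose sample in SAP 8.1 is 15 minutes after the infusion ends. If the rat half-lives held in humans, 0.5^(0.25/0.66) = 77% to 0.5^(0.25/1.17) = 86% of the end-of-infusion level would remain. Protocol 7.2.5 also schedules MAD samples during the infusion. Cell binding of 90% or more does not show that whole profiles at 1.0 mg will be BLQ.

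**No formal dose comparison is touched.** This also stands. A reader might infer that the rule flattens the dose-proportionality slope. The documents do not support that: the power model uses the PK Parameters Population, which has its own data-sufficiency rule. Changing SAP 5.3 alters no slope or confidence interval. The ratios in the table above concern comparison of descriptive means by eye.

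**The benchmark is itself biased.** True BLQ values lie between zero and the quantification limit, so a mean that scores them as zero is too low. The percentages therefore measure inconsistency with the SAP's own convention, not error against the truth.

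**An all-BLQ profile may be an error.** Protocol 3.5 says the peptide cannot be detected in whole blood without phosphoric acid, so mishandled samples could give false zeros. This is a good reason to exclude documented failures. It does not justify excluding every all-BLQ profile without inquiry.

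**The exclusion is already visible.** Largely so. Listings use the ITT Population and display BLQ, enrolment listings flag inclusion in the population, and the SAD disposition shell counts it. The MAD disposition shell names only a Pharmacokinetic Population. Visibility does not correct the summaries.

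**Geometric statistics would fail.** A retained all-BLQ subject puts a zero at every time point, and a geometric mean cannot take zeros. The objection is right that a change to SAP 5.3 alone is not enough. The gap already exists wherever a BLQ value is set to zero, because the SAP has no rule for it.

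**Conclusion.** The point holds as a conditional flaw in the descriptive concentration tables and mean plots. SAP 5.3 selects on the measured outcome and conflicts with the BLQ = 0 rule in SAP 8.3. The direction is certain under that rule: arithmetic means rise or stay the same. With six recipients and complete sampling, the rise is 20%, 50% or 100% for one, two or three all-BLQ recipients, and nil for none.

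The rule applies at every summarised dose. All-BLQ profiles are most likely at 1.0 mg, in both SAD and MAD, because it is the lowest dose summarised. It would overstate the case to read the percentages as a forecast for this trial, since no quantification limit or BLQ rate is given. The change is worth making because it is cheap and is best fixed before the data are seen; no formal conclusion of the trial depends on it.

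**What to change.** - **SAP 5.3:** define the PK Concentration Population as all subjects who receive any LSALT and have at least one valid assayed post-dose sample, quantifiable or not. Exclude only samples or profiles with a documented dosing or sample-handling failure.
- **SAP 8.3 and the concentration table shells:** keep BLQ = 0 for arithmetic summaries and mean plots, and report the number BLQ at each time point. State that the geometric mean and geometric CV are calculated on quantifiable values only, with their n shown.
- **Disposition shells:** count the PK Concentration Population in the MAD table as in the SAD table, and report how many in each dose group had no quantifiable value.
- **SAP 5.4:** no change.

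The cost is a revised clause in SAP 5.3, one extra rule for geometric statistics and small shell edits. If any profile is all-BLQ, the arithmetic means will be somewhat lower and more variable, and the geometric means will describe quantifiable values only and should be labelled so.
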